8.8. Other Study Supplies

Aclaris Therapeutics, Inc. or a third party will provide:

- Equipment, supplies and training for taking standardized photographs
- Equipment and training for SALT and ALODEX assessments
- Equipment, supplies and training for capture of ECGs for central reading
- Scales for weighing the study medication bottles
- Supplies and shipment instructions of PK and PD samples
- UPT kits

8.9. Blinding

Blinding of study medication is important for validity of this study. This study uses a double-blind design for the initial 28-day double-blind treatment period. The study medications used during the double-blind period are indistinguishable in appearance, as packaged and labeled.

8.9.1. Unblinding the Study Medication (Double-blind Period)

The blinding may be broken in the event of a medical emergency, in which knowledge of the study medication identity is critical to the management of the subject's course of treatment. Before breaking the blind, the investigator shall determine that the information is necessary (*i.e.*, that is, will alter the subject's immediate course of treatment). In many cases, particularly when the

emergency is clearly not study medication-related, the problem may be effectively managed by assuming that the subject is receiving an active study medication without the need for unblinding.

If the investigator deems it necessary to break the blind for a study subject, he/she will attempt to contact the Medical Monitor (protocol page 1) to obtain concurrence. If it is not possible to contact the Medical Monitor beforehand, contact her/him as soon as possible after breaking the blind for a subject.

To identify a subject's study medication, locate the second panel of the tear-off label from the Subject Kit attached to the subject's study medication label page, and follow the instructions on the label. Record the date of unblinding, the reason for unblinding, and the initials of the investigational staff member who performed the unblinding on the subject's study medication label page. Any subject whose blind has been broken must be discharged from the study (Section 6.8). Subject must complete the double-blind treatment period to be eligible for entry into the open-label extension.

At the end of the study, the original study medication label page will be returned to Aclaris Therapeutics, Inc. with a photocopy placed in the investigator's study file. The original study medication label page will be available, upon request, to the site if needed to respond to a regulatory audit.

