On Day 29 (Visit 7) subjects who complete Visit 7, continue to meet the entry criteria, have no clinically significant AEs or tolerability issues and in the opinion of the investigator have experienced or are capable of re-growing scalp hair will be eligible to enter a 12-month open-label extension. In the open-label extension, safety, tolerability and efficacy will be assessed. All subjects enrolled in the open-label extension will apply ATI-50002 Topical Solution, 0.46% to the entire scalp, twice daily for 52 weeks (12 months). In addition, subjects with eyebrow loss may apply a thin film of study medication to the affected eyebrow(s) twice-daily for 52 weeks (12 months). Subjects will be followed for safety, tolerability and efficacy as detailed in Section 7.3. Subjects who decline or are not eligible for the open-label extension should be seen for the Visit 16 (Post-treatment) assessments 30 days following the Day 28 (Visit 6). The duration of the open-label extension (OLE) should be based on the date of the visit that the subject initiated OLE treatment rather than the days from Baseline (Visit 2). For subjects who entered the open-label extension and had a gap between Visit 7 and entry into the open-label extension due to an administrative delay total study participation may be longer than 400 days.

Number of Subjects (planned):

12 subjects will be enrolled into the study.

Number of Study Sites:

This study will be conducted at two clinical sites.

Inclusion Criteria:

Subjects must meet all the following criteria to be eligible for participation in the study.

1. Able to comprehend and willing to sign an Informed Consent Form (ICF).
2. Male or non-pregnant, non-nursing female ≥ 18 years old at the time of informed consent.
3. Have a clinical diagnosis of stable, clinically typical, alopecia universalis or alopecia totalis.
4. Have a duration of the current episode of AU or AT for a minimum of 6 months and a maximum of seven years.
5. Have $> 95\%$ total scalp hair loss as measured by the Severity of Alopecia Tool (SALT).
6. If a woman of childbearing potential (WOCBP), must have a negative serum pregnancy test at Screening (Visit 1) and a negative urine pregnancy test (UPT) at Baseline (Visit 2) and agree to: use a highly effective method of birth control for the duration of the study; not be planning a pregnancy during the study duration and use contraception for 30 days after last application of study medication (Refer to Section 11).

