
16. Participation in an investigational drug or device trial in which administration of an investigational study drug or device occurred within 30 days or 5 half-lives (whichever is longer) of Screening (Visit 1). Subjects who have participated in a study of an investigational drug, device or biologic agent for alopecia areata (AA, AU or AT) within 1 year of screening will be eligible to participate only with individual permission from the Medical Monitor.
 
17. Sensitivity to any of the ingredients in the study medications.
 
18. History of or current alcohol or drug abuse within 2 years of assessment for study enrollment.
 
19. Screening ECG findings of:
 
 • QTcF >450msec for males or >470msec for females (use of the ECG algorithm is acceptable for this purpose) • Heart rate < 45 or > 100 beats/minutes (inclusive) • Rhythm disturbance other than sinus arrhythmia or ectopic supraventricular rhythm (ectopic atrial rhythm) • Conduction disturbance including PR >240msec, pre-excitation (delta wave and PR <120msec), second degree or higher AV block • Acute or chronic signs of ischemia • Left Bundle Branch Block • Prior myocardial infarction 		

Duration of Treatment
 
Double-blind Treatment
 
Screening period up to 30 days.
 
Double-blind treatment period is 29 days (maximum of 28 days of study medication application).
 
Post-treatment Visit 16 is up to 33 days (30 +3 days) following Day 29 for subjects not continuing into the open-label extension.
 
Total study participation for subjects from Baseline (Visit 2) through Post-treatment Visit 16(Day 59 + 3 days) is up to 62 days (29 + 33).
 
Double-Blind + Open-Label Extension
 
The duration of the total study participation from Baseline (Visit 2) to Week 56 (Visit 16) is anticipated to be a maximum of 400 days (393 + 7 days).
 
The duration of the open-label extension (OLE) should be based on the date of the visit that the subject initiated OLE treatment rather than the days from Baseline (Visit 2). For subjects who entered the open-label extension and had a gap between Visit 7 and entry into the open-label extension due to an administrative delay total study participation may be longer than 400 days.
		

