6.8. Subject Withdrawal Criteria

Subjects will be informed that they are free to withdraw from the study at any time and for any reason. The Investigator may remove a subject from the study if, in the Investigator's opinion, it is not in the best interest of the subject to continue the study. Examples of other reasons subjects may be discontinued from the study are: a change in compliance with an inclusion or exclusion criterion, occurrence of AEs, occurrence of pregnancy or use of a prohibited therapy. The Investigator or designee must inform the Aclaris Therapeutics, Inc. study monitor of any subject discontinuation. (Refer to Section 10.2.4 for study medication discontinuation or termination criteria).

In case of premature discontinuation of study participation, all efforts will be made to perform all Week 56 (Visit 16) assessments. The date the subject is withdrawn from the study and the reason for discontinuation must be recorded in the subject's electronic case report forms (eCRFs). All withdrawn subjects with ongoing AEs will be followed until the event has resolved or stabilized, until the subject is referred to the care of a local health care professional, or until a determination of a cause unrelated to the study medication or study procedures is made.

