On Day 29 (Visit 7) subjects who complete Visit 7, continue to meet the entry criteria and have no clinically significant AEs or tolerability issues will be eligible to enter a 12-month open-label extension. In the open-label extension, safety, tolerability and efficacy will be assessed. All subjects enrolled in the open-label extension will apply ATI-50002 Topical Solution, 0.46% to the entire scalp, twice daily for 52 weeks (12 months). In addition, subjects with eyebrow loss may apply a thin film of study medication to the affected eyebrow(s) twice-daily for 52 weeks (12 months). Subjects will be followed for safety, tolerability and efficacy as detailed in Section 7.3. Subjects who decline or are not eligible for the open-label extension should be seen for suture removal, if applicable per Section 7.3 and Visit 16 (Post-treatment) 30 days \pm 3 days following the Day 28 (Visit 6). Subjects enrolled in the initial 6-month Open Label Extension outlined by Protocol Amendment 1 (dated 06Feb2018) must be re-consented under Protocol

Amendment 2 (dated 14AUG2018) in order to continue for an additional 6 months of Open Label treatment.

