¹⁷ On Day 29 (Visit 7) subject may be given the option to move into open-label extension treatment. 
 • If the subject declines the open-label extension, she/he should be seen for the Visit 16 (Post-treatment) assessments 30 days following the date of Day 29 (Visit 7). • If the subject chooses to continue in to the open-label extension, she/he must sign an ICF prior to being dispensed open-label drug and receiving continued study medication application instructions. • If the subject enrolls in open-label treatment after Day 29 (Visit 7), an unscheduled visit will be conducted in order to obtain consent, review drug application instructions, and dispense drug. This will be considered the official date that the subject initiated open-label extension treatment and the scheduling of subsequent visits 8-16 should be based off of this date as referenced by (OLE xxx) in the treatment day schedule header above. 											
¹⁸ Subjects who are eligible and consent to enter the open-label extension will have a baseline CEA and SEA completed at Visit 7 or the unscheduled Visit.											

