8.6. Dose Modification

Subjects should be instructed not to modify the study medication application procedure or frequency. All application modifications must be reported on the appropriate source document

and eCRF. If the subject experiences any significant application site AE(s), after discussion with the Sponsor, the investigator or designee may direct the subject to reduce study medication application frequency to once a day. Every effort should be made to resume twice daily applications for the week prior to Day 28 (Visit 6). If a subject cannot resume twice-daily applications to the scalp for more than 4 consecutive days, the subject must be removed from the study. Refer to Section 10.2.4 for Study Medication Interruption or Discontinuation due to related SAEs or specific abnormal laboratory values.

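### Emergency unblinding ends study participation, not only dosing, so the subject's remaining planned double-blind safety assessments are forgone

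*Protocol*

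**What the plan says.** Protocol Section 8.9.1 allows the blind to be broken when knowing the assignment is critical to managing a medical emergency. The consequence is stated without exception: "Any subject whose blind has been broken must be discharged from the study (Section 6.8"). The same paragraph adds: "Subject must complete the double-blind treatment period to be eligible for entry into the open-label extension".

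Section 6.8, to which the rule points, provides: "In case of premature discontinuation of study participation, all efforts will be made to perform all Week 56 (Visit 16) assessments". It also has withdrawn subjects with ongoing adverse events followed until the event settles, care passes to a local professional, or a cause unrelated to the study is established.

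For a subject outside the extension, the schedule in Section 7.3 places post-dose laboratory tests and ECGs at Visit 5 (Day 15), Visit 7 (Day 29) and Visit 16. Sections 9.5.2 and 9.5.5 confirm the Day 29 examination and the Day 15 and Day 29 ECGs. Vital signs are due at every visit (Section 9.5.1).

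Section 8.6 has a separate removal rule: "If a subject cannot resume twice-daily applications to the scalp for more than 4 consecutive days, the subject must be removed from the study".

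SAP 4.1.1 keeps every dosed subject in the As-Treated population. SAP 4 imputes nothing except missing dates.

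**The concern.** Safety is part of the primary objective, and the rule applies only to a subject who has had a medical emergency. Planned observation is therefore cut back for the subject in whom it is of most interest. Discharge does not restore the blind: staff already know the assignment. Nor does that knowledge invalidate a central laboratory value (Section 9.5.3) or a centrally processed ECG (Section 9.5.5).

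Elsewhere the protocol separates stopping the drug from leaving the study. Section 10.2.4.2 requires only permanent discontinuation of medication after, for example, anaphylaxis or symptomatic herpes zoster, and Section 10.2.4.1 arranges retesting while medication is interrupted. Yet if one of those events also led to a code break, Section 8.9.1 would end participation. It gives no reason for ending observation as well as dosing.

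At stake are the by-visit laboratory and vital-sign summaries and the completeness of the laboratory and ECG shift tables. No test or power figure is affected.

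**Working it through.** **The plan's own figure.** The Synopsis randomizes 12 subjects 2:1. 12 × 2/3 = 8 on ATI-50002 and 12 × 1/3 = 4 on vehicle, which matches the stated split. Section 12.1 gives no power calculation, so there is none to reproduce.

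**Scheduled sets at stake.** The inputs are the post-dose laboratory/ECG visits in Section 7.3 for a subject outside the extension: Visit 5, Visit 7 and Visit 16, three sets in all. Under Section 8.9.1 the double-blind visits after the code break fall away. Visit 16 remains on a best-efforts basis under Section 6.8.

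| Blind broken | Laboratory/ECG sets forgone | Visit 7 examination |
|---|---|---|
| Before Visit 5 | Visits 5 and 7: 2 of 3 | forgone |
| Between Visits 5 and 7 | Visit 7: 1 of 3 | forgone |
| After Visit 7 | none: 0 of 3 | already done |

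Vital signs are also forgone at whichever of Visits 3 to 7 are still to come.

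**Share of an arm.** One subject is 1/8 = 12.5% of the active arm or 1/4 = 25% of the vehicle arm. With full arms and no other missing data, the by-visit count falls from 8 to 7 or from 4 to 3. Section 6.7 rules out replacement, and values are not imputed.

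**What is kept.**
- The schedule's Visit 16 column includes laboratory tests, ECG, vital signs, physical examination and adverse events. Section 9.5.2 names the Visit 16 examination only for extension subjects, although the schedule marks it without that limit.
- SAP 4.4.4 counts a follow-up ECG in the double-blind shift table when the subject did not enter the extension. SAP 4.4.5 takes the worst post-baseline laboratory value and does not exclude follow-up visits.
- The triggering event is tabulated in the As-Treated population. Sections 6.8, 10.2.1 and 10.2.2 continue the follow-up of ongoing events, related events and serious events respectively.

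**When Visit 16 happens.** Section 6.8 does not say. Other passages give a date:
- Synopsis, Open-Label Extension: "should be seen for the Visit 16 (Post-treatment) assessments 30 days following the Day 28 (Visit 6"), so 28 + 30 = Day 58.
- Synopsis, Duration of Treatment: "Post-treatment Visit 16 is up to 33 days (30 +3 days) following Day 29 for subjects not continuing into the open-label extension", so nominally 29 + 30 = Day 59.
- Section 7.1: "Subjects who decline or are not eligible for the open-label extension should be seen for suture removal, if applicable", followed by a Visit 16 date again counted from Day 28.
- Section 7.3, footnote 17: "she/he should be seen for the Visit 16 (Post-treatment) assessments 30 days following the date of Day 29 (Visit 7"), again Day 59.

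These are written for subjects who decline, are not eligible for, or do not continue into the extension. They count from Day 28 or Day 29, when a discharged subject may already have left. They may be borrowed for an early exit, but the protocol does not say so.

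**The case against.** The strongest reply is that the cited section already deals with the matter. Section 6.8 seeks a full Visit 16 set, and clinically significant laboratory or ECG abnormalities are themselves adverse events (Sections 9.5.3 and 9.5.5), so ongoing ones are followed. The trigger is narrow: the information must alter immediate treatment, the Medical Monitor's agreement is sought, and sites are told that many emergencies can be managed by assuming active drug. Most of this stands. It limits the point to the planned double-blind timepoints and keeps it small. It does not remove the point, because no text retains those timepoints.

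A reader might infer more than the documents support:

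- **All later safety data are lost.** Section 6.8 and the SAP's follow-up rules contradict this.
- **A gap of weeks in laboratory tests and ECGs, together with uncollected new adverse events.** These need opposite readings. If Visit 16 is at Day 58 or 59, a subject unblinded on Day 10 waits 58 − 10 = 48 or 59 − 10 = 49 days for the next scheduled set, but adverse-event reporting continues until that visit. If the set is done at discharge, reporting may stop early, but the laboratory tests and ECG are done at once. Any early end to reporting comes from Sections 6.8 and 10.1.4 and affects every early exit, so it is not a consequence of the unblinding rule.
- **Completion of the double-blind period is all that keeps such a subject out of the extension.** The Synopsis and Section 7.1 also require continued eligibility and no clinically significant adverse event, which a subject with an emergency would very likely fail.
- **The safety comparison is biased in a known direction.** Nothing in the documents shows which way one subject's missing values would move it.

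It can also be said that Section 10.2.3 withdraws subjects from the study for ECG findings, so changing only the code-break rule is selective. That is fair as far as it goes. The proposed change leaves that rule as it is, but this is no reason to keep the code-break rule.

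**Conclusion.** The point holds in limited form. Section 8.9.1 ends participation rather than dosing alone. The subject forgoes 2 of 3 scheduled post-dose laboratory/ECG sets if unblinded before Visit 5, or 1 of 3 between Visits 5 and 7, with the Visit 7 examination and the vital signs still due. The offset in Section 6.8 is real but partial: one best-efforts set with no stated timing, plus event follow-up.

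The consequence is small. It concerns a rare subject, 12.5% or 25% of an arm, in summaries that are purely descriptive; SAP 4.8 drops even the planned adverse-event test. The documents give no frequency of unblinding, so no expected loss can be calculated. The counts assume a subject who would otherwise have attended Visits 5, 7 and 16 and not entered the extension. This is a cheap improvement to safety follow-up, not a flaw that threatens a conclusion.

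**What to change.** In Section 8.9.1, replace the discharge requirement with wording to this effect:

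*A subject whose blind is broken permanently stops study medication and cannot enter the open-label extension but, with consent, remains in the study for the safety assessments already scheduled (adverse events, vital signs, laboratory tests, ECG, physical examination) through Visit 7 and the post-treatment Visit 16. The Section 8.6 removal rule does not apply. No further PK or PD biopsies or PK blood samples are taken.*

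The Section 8.6 exception is needed because, read literally, that rule would remove the subject after more than 4 consecutive days off twice-daily application. The explicit extension exclusion avoids doubt, since a subject who stays through Visit 7 might be argued to have completed the period. Flag post-unblinding data in the listings and keep them in the safety tables.

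I would not add a minimum interval before Visit 16 to Section 6.8. Applied to every early exit, it could delay a prompt exit laboratory/ECG set, including for subjects withdrawn under Section 10.2.3.

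The cost is one replaced passage, matching consent wording and a listing flag. For the subject it means a few visits already on the schedule. Some adverse-event reports will be made with knowledge of the assignment, which the flag makes visible.

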8.10. Study Medication Packaging, Labeling, Storage and Security

The study medication must be used by the study subjects only. Investigational site staff will explain the application of the study medication to subjects.

Study medication will be provided by Aclaris Therapeutics, Inc. and labeled according to regulations. Study medications must be stored in a secure area with limited access under appropriately controlled and monitored storage conditions. Study medication should be stored at controlled room temperature 59°F - 77°F (15°C – 25°C). Subjects will be instructed to store the study medication in the original glass bottle (in the carton provided) at room temperature, away from heat, moisture, direct light, and to keep it from freezing and out of the reach of children.

The study medication will be supplied in amber glass 120 mL bottles. Disposable droppers with 1 mL calibration mark will be provided in the study kits. During the open-label portion of the study, applicators will also be provided for application of the ATI-50002 Topical Solution, 0.46% to the eyebrow(s).

For the double-blind period, one Subject Kit box will contain 6 bottles in individual boxes and disposable droppers. Each kit will be labelled with a two-part, three panel, double blind label. One part (one-panel) of the label remains attached to the Subject Kit, the other part (two-panel tear-off) is separated and attached to the subject's study medication label page when the subject is randomized. Each box and bottle will be labeled with a single panel label.

For the open-label period, subjects will receive 1-3 bottles of ATI-50002 Topical Solution, 0.46% per month. Each bottle is packaged in a carton and both the bottle and carton will be labelled with a single-panel label.

9. STUDY ASSESSMENTS

The study assessments will be performed according to the schedules noted below by the investigator, an appropriately trained study staff member or the subject as noted for each assessment. The SALT and ALODEX assessments should be performed by the same staff member for a given subject throughout the study. If this is not possible, an appropriate designee with overlapping experience with the subject and study should perform the assessments. Hair regrowth in subjects is not anticipated during the 28-day duration of the double-blind study medication application.

9.1. Efficacy Assessments

9.1.1. Severity Alopecia Tool (SALT) Score

The SALT score is a measurement of the amount of scalp without any hair. The Investigator will assess the SALT score using an iPAD provided by Aclaris at Baseline (Visit 2), Day 29 (Visit 7), and as detailed in Section 7.3 for the subjects who continue in the open-label extension. Equipment, supplies, training and a detailed Reference Guide will be provided to the investigational site prior to the initiation of subject enrollment.

